Length of Cook Catheter Placement and Induction of Labor

NCT04233008

Version date 2/21/18

Partners Human Research Committee Detailed Protocol

[name]
[name] (principal investigator)

Study Title: Length of foley catheter placement and induction of labor: a randomized controlled trial

Version date 2/21/18

Background and Significance

Induction of labor occurs in 24% of pregnancies in the United States (Hamilton). There are many maternal and fetal indications for induction of labor at various gestational ages of pregnancy. Induction of labor consists of initial cervical ripening followed by oxytocin. Cervical ripening helps the cervix soften, thin and dilate. There are multiple agents for cervical ripening including pharmacologic and mechanical dilation. Pharmacologic agents include prostaglandins and oxytocin. Mechanical ripening most commonly refer to a foley catheter balloon device. Mechanical methods have been associated with lower rates of cesarean section compared with oxytocin alone (Boulvain). Previous studies have compared foley catheter placement for 12 vs. 24 hours and showed 12 hours decreases time to delivery (Cromi). Recently, studies have looked at the efficacy of dual induction agents with combination of oxytocin and foley catheter with time to delivery (Levine).

The cook catheter device, a type of foley catheter used for mechanical dilation, is a silicone double balloon catheter that can be inflated to 80mL/balloon. Per device guidelines it should not be left in place for more than 12 hours. Given these instructions the balloon is most often removed at 12 hours or spontaneously when it falls out given cervical dilation during the induction process.

Currently there are no studies that evaluate the time to delivery in women with the foley catheter removed at 6 hours vs. 12 hours. Our theory is that the benefit of the foley catheter is within the first 6 hours and we will study whether there is faster time to delivery in this intervention group.

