This study has potential benefits for both individuals, hospital efficiency, and healthcare costs in the future. Longer inductions are associated with higher rates of postpartum hemorrhage and infection, therefore decreasing induction length would hopefully limit these labor complications. By decreasing the length of time for induction of labor, hospital and efficiency and healthcare costs would likely improve. Patients in the future would benefit from the knowledge gained in this trial if labor inductions are shorter with only 6 hours of a foley catheter placement and labor induction protocols change as a result.

Specific Aims

The objective of our study is to compare the time to delivery in women who undergo induction of labor with foley catheter and oxytocin for six vs. twelve hours. Our

hypothesis is women who undergo an induction with foley catheter for 6 hours will have a shorter time to delivery.

Subject Selection

Our study population will include women 18-50 years of age at term (37-41 6/7 weeks) with a singleton gestation in cephalic presentation who are undergoing induction of labor. Both nulliparous and multiparous women will be included. Women will need to have a bishop score <6 or cervical dilation <2cm with intact membranes to be included, as these are the women currently being offered cervical ripening prior to labor induction. Women will be excluded if there is a contraindication to vaginal delivery. Women with history of a prior cesarean section will be excluded given their management may differ after removal of the foley catheter. Non-English speaking women will also be excluded given the length of time for induction on labor and delivery and inability to guarantee 24 hour interpreter services.

Women will be recruited from the Maternal Fetal Medicine and general Obstetrics clinics at Brigham and Women's Hospital. They will be counseled in the office by their provider when an induction of labor is discussed, based on their cervical examination.

Subject Enrollment

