The foley catheter will then be removed at 6 vs. 12 hours based on randomization. At that point health care providers will manage active labor per usual practice. Pitocin will be continued after foley removal, as is standard practice and health care providers may perform amniotomy at any point during the induction process with a recommendation for amniotomy when cervix more than 4cm dilated, consistent with literature demonstrating a shorter time to delivery with earlier amniotomy (Battarbee). Labor interventions are at the discretion of the healthcare provider. The participants will have continuous fetal monitoring throughout their induction, labor and delivery. The need for operative delivery or cesarean section will be at the discretion of the healthcare provider.

Biostatistical Analysis

The main outcome will be length of time to delivery. A subject's participation will end with outcomes 4 weeks following delivery.

Secondary maternal outcomes will be measured including cesarean delivery rate, time to active labor (>5cm dilated), delivery within 12 hours, delivery within 24 hours, maternal length of stay, and indication for cesarean delivery. We will also calculate a composite maternal morbidity outcome including estimated blood loss, higher-order laceration, blood transfusion, endometritis, wound infection, venous thromboembolism, hysterectomy, ICU admission or death. These outcomes will also be stratified by parity. We will also evaluate rates of analgesia in both groups.

A composite neonatal morbidity will be calculated including culture-proven neonatal sepsis, neonatal blood transfusion, hypoxic-ischemic encephalopathy, intraventricular hemorrhage grade 3 or 4, or therapeutic hypothermia. We will also analyze NICU admission, NICU admission for greater than 48 hours, and neonatal length of stay.

In the literature, the mean time to delivery with an induction of labor is 18 hours. A four hour reduction in time to delivery is considered clinically meaningful and has been used in prior studies evaluating induction of labor (Levine). A Type I α error of 0.05

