was selected. Assuming 80% power and a two-sided P value we would need 71 participants in each group for total sample size 142. However, given that some patients will undergo cesarean section during their induction of labor, we will exclude cesarean section in a sensitivity analysis. Assuming that 20% of patients will have a cesarean section, we will include 89 women in each arm, 178 women total. For statistical purposes, intent to treat analysis will be performed. Non-parametric measures will be used for statistical analysis. These models will also be adjusted for parity.

Risks and Discomforts

Women may experience discomfort with foley catheter insertion, which will be handled with pain medication in a similar way to current practices on labor and delivery.

Because the foley catheter is routinely used for cervical ripening during labor induction on labor and delivery we think that there is minimal increased risk from the study. However, by limiting the foley catheter to 6 hours, the length of time of cervical ripening is limited. Upon removal of the catheter at 6 hours the cervix may not be ripened and therefore increase the risk of prolonged induction and ultimately cesarean section. If the intervention group is associated with longer length of time to delivery it may also be associated with increased blood loss and risk of infection, which are known risks of prolonged induction. Our study, however, allows physicians to manage labor as deemed appropriate after foley removal. Thus, if cervical ripening is felt to be inadequate, alternative cervical ripening agents (such as misoprostol) could still be used in appropriate candidates. Moreover, we feel it is most likely that the 12-hour foley group (the current standard of care) will have longer labor inductions, not the 6-hour experimental group, consistent with prior studies showing that labors were longer with 24 hour foley placement rather than 12 hour placement (Cromi). Also, our clinical experience is that when foley balloons are actively managed (i.e. the patient is checked vaginally sooner than 12 hours and tension is applied to see if the foley is ready to come out) most women achieve adequate cervical dilation much sooner than the maximum of 12 hours.

Potential Benefits

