Because this study is a randomized controlled trial, there is no direct benefit to individuals. Given the nature of the study we do not know if, and which treatment is better. Furthermore, the study is randomly allocated so there is an equal chance of the patient being in either treatment arm.

There are however many benefits for the healthcare system in the future. By determining the faster method for induction of labor we may find that risk of infection and blood loss are lessened. The fetus also benefits by shorter induction times by limiting the time of intrauterine stress during labor and delivery. Healthcare cost would benefit from the information gained in this study by decreasing hospital stays. Currently, the most effective method of inducing labor remains unknown.

Monitoring and Quality Assurance

The principal investigator will review the entries for each participant to ensure they are complete. We will not perform any interim analysis, as we feel there is minimal risk from the study protocol and would not stop the study early. When adverse events

occur they will be reported to the Partners' IRB within 5 days with a detailed description of the event as described in the guidelines for adverse events reporting. Serious adverse events (severe hemorrhage, maternal death, neonatal death, neonatal hypoxemic encephalopathy) will be reviewed by the head of labor and delivery and the study staff to ensure the outcome is not related to the study protocol.

References

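### Does the plan need a stated commitment to record and report actual catheter time by arm?

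*Combined protocol and SAP*

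**What the plan says.** Specific Aims sets out to "compare the time to delivery in women who undergo induction of labor with foley catheter and oxytocin for six vs. twelve hours". Study Procedures has one sentence on the randomized difference: "The foley catheter will then be removed at 6 vs. 12 hours based on randomization". Oxytocin is given to both groups, and care after removal is left to the provider.

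Two places suggest that actual catheter time may be shorter than assigned time. Background and Significance describes usual practice, in which "the balloon is most often removed at 12 hours or spontaneously when it falls out". Risks and Discomforts reports the team's experience that, under active management, "most women achieve adequate cervical dilation much sooner than the maximum of 12 hours".

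Biostatistical Analysis makes time to delivery the main outcome and then lists the others: "Secondary maternal outcomes will be measured including cesarean delivery rate, time to active labor (>5cm dilated), delivery within 12 hours, delivery within 24 hours", followed by length of stay, indication for cesarean, maternal and neonatal morbidity and analgesia. Catheter time, mode of exit and adherence are not on the list. On the analysis set it says: "For statistical purposes, intent to treat analysis will be performed". Monitoring and Quality Assurance adds: "The principal investigator will review the entries for each participant to ensure they are complete". It does not say what the entries are.

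**The concern.** A trial of 6 against 12 hours of catheter time would normally show how many hours each arm received. If many balloons are out by hour 6, the arms receive similar exposure whatever was assigned. A null result on time to delivery would then have at least two readings: earlier removal does not help, or the arms hardly differed in catheter time. The first would count against earlier removal in general. The second would apply only to units where balloons come out equally early. None of the listed outcomes separates the two; reaching more than 5 cm does not date the exit of the balloon. Potential changes to induction practice are part of the stated rationale, so another unit would want to know the separation achieved, after a positive result as well.

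**Working it through.** **The plan's own figure.** Biostatistical Analysis states 71 per arm, raised to 89 for a 20% cesarean rate: 71 / (1 − 0.20) = 88.75, rounded up to 89. The inflation reproduces. The 71 itself cannot be checked because no standard deviation is given. Catheter time does not enter the calculation.

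**How much separation could be lost.** Inputs: assigned removal at 6 or 12 h (Study Procedures). The share of catheters still in place at each hour is not in the documents and is assumed here. Every woman is taken to have a catheter placed, and removal is taken to happen at the assigned time unless the balloon is already out.

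Let S(t) be the share that would still be in place at hour t without planned removal. Then

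mean difference = area under S(t) from 6 to 12 h.

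With a constant exit rate and a share p in place at hour 6, the share at hour 12 is p², the rate is r = −ln(p)/6, and the difference is (p − p²)/r.

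| In place at 6 h / 12 h | r per hour | Mean difference |
|---|---|---|
| 100% / 100% | 0 | 6.0 h |
| 90% / 81% | 0.01756 | 0.09 / 0.01756 = 5.1 h |
| 75% / 56% | 0.04795 | 0.1875 / 0.04795 = 3.9 h |
| 50% / 25% | 0.1155 | 0.25 / 0.1155 = 2.2 h |

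If all catheters are in place at hour 6 and half come out evenly between 6 and 12 h, the difference is 6 × (1 + 0.5)/2 = 4.5 h. The range is wide, and the documents do not say where in it the trial would fall.

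**Whether the table would be informative.** For the same exit curves, the standard deviations of catheter time in the 6-hour and 12-hour arms are 1.07 and 2.87 h at p = 0.90, and 2.06 and 4.28 h at p = 0.50. With 89 per arm, the 95% half-width is 1.96 × √((SD₁² + SD₂²)/89), which gives 0.64 h and 0.99 h. A table drawn from charts would therefore tell good separation from poor.

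**What the text supports.** The statement in Background and Significance concerns usual practice and gives no rate. The statement in Risks and Discomforts concerns adequate dilation under active management, meaning earlier checks with tension. Study Procedures prescribes gentle traction and removal at the assigned hour and does not prescribe those earlier checks. Neither statement says anything about hour 6. Some early exit is plausible; its extent is unknown.

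**What the planned analysis needs.** Intent to treat compares women as assigned. Early expulsion is part of what happens under each policy, and it does not bias that comparison. Exit times are needed to describe and interpret the result, but not to compute it.

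**Why no power figures are given.** A loss of power follows only if the 4 h target is taken to apply solely to women still holding the catheter at hour 6. The documents do not say so. Read as an average over all randomized women, the 4 h already includes any dilution.

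**The case for a change.** The strongest case for a change is that the exposure is the experiment, the protocol itself acknowledges spontaneous exit, and an open-ended outcome list commits nobody to anything. The trial is unblinded, and women may be randomized in clinic up to about a week before induction, so some might never have a catheter placed. A few chart fields and one table would cost almost nothing and would leave allocation, sample size and main analysis as they are.

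Much of this stands. No section names the item, it is cheap, and a good report would include it, with women who never had a catheter shown separately. But if the times are charted, which is likely for a timed removal on a labor unit though not stated, they can be extracted later and the two readings told apart without any prior commitment. Nor would the table settle a null result. Imprecision and discretionary care after removal, including other ripening agents, are rival explanations that it does not address. A comparison restricted to women still holding the catheter at hour 6 would select on an event after randomization and would be weak evidence. What remains is a reporting preference, not a fault in the design or analysis.

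**Conclusion.** No change to the plan is called for. The outcome list omits actual catheter time, exit mode and adherence, but this is missing detail that analysts would fill sensibly: whoever reports a trial of catheter duration will be expected to show catheter hours by arm. The comparison of assigned policies, which is what Specific Aims asks for, is sound at any degree of separation, and no stated figure or rule is wrong.

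The possible loss of separation runs from none (6.0 h) to substantial (2.2 h with half the catheters out by hour 6). It rests entirely on assumed exit rates, so it shows what could happen, not what the plan implies. The conclusion also assumes that insertion and exit times are charted in routine care. If they were not, the two readings of a null result could not be separated afterwards, although the main comparison would still be valid.

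### The cesarean-excluded sensitivity analysis selects women on a post-randomisation outcome, and no planned analysis measures time to vaginal delivery in all randomised women

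*Combined protocol and SAP*

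**What the plan says.** All references are to the combined protocol and SAP.

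- **Aim.** Specific Aims states the "hypothesis is women who undergo an induction with foley catheter for 6 hours will have a shorter time to delivery". The main outcome in Biostatistical Analysis is time to delivery, with no route specified.
- **Main analysis.** "For statistical purposes, intent to treat analysis will be performed", using non-parametric methods adjusted for parity.
- **The exclusion.** The plan says: "given that some patients will undergo cesarean section during their induction of labor, we will exclude cesarean section in a sensitivity analysis". The sample is enlarged on this account: "Assuming that 20% of patients will have a cesarean section, we will include 89 women in each arm, 178 women total".
- **Secondary maternal outcomes.** These include "cesarean delivery rate, time to active labor (>5cm dilated), delivery within 12 hours, delivery within 24 hours" as well as "maternal length of stay, and indication for cesarean delivery". The 12- and 24-hour outcomes are not limited to vaginal delivery. No rule treats cesarean as censoring or as a competing event.
- **How cesarean arises.** Subject Enrollment says neither patients nor providers are blinded. Study Procedures leaves the cesarean decision to the provider.
- **Expected effect of treatment.** Risks and Discomforts says that after removal at 6 hours "the cervix may not be ripened and therefore increase the risk of prolonged induction and ultimately cesarean section". The same section also says "we feel it is most likely that the 12-hour foley group (the current standard of care) will have longer labor inductions".

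**The concern.** Dropping women by mode of delivery conditions on something that happens after assignment and that assignment may change. The women who remain in each arm need not be alike at baseline, so a difference in their times cannot be credited to the assigned duration as the primary result can.

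The analysis matters because the any-route primary counts an early cesarean as a short time to delivery. A reader who wonders whether cesareans explain the time result will turn to the one analysis that takes route into account, and that is the analysis randomisation does not protect. If cesarean tends to follow slow labor, the slower arm loses more of its slowest labors and the difference in hours shrinks, whichever arm is slower. If one arm has more cesareans for some other reason, that arm can appear faster when it is not.

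The other planned outcomes help but do not fill the gap. Cesarean rate and indication carry no time. Time to active labor carries no route, and it is incomplete when cesarean comes before the dilation threshold.

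**Working it through.** **1. The plan's own figures.** Inflation: 71/(1 − 0.20) = 88.75, rounded up to 89 per arm, 178 in total. This reproduces.

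The documents give no SD. Solving the two-sample formula at two-sided 0.05, 80% power and a 4 h difference gives SD = 4/√((1.96 + 0.8416)² × 2/71) = 8.51 h. With all 89 per arm and SD 8.5 h, power is Φ(4/(8.5 × √(2/89)) − 1.96) = Φ(1.18) = 0.88 (t-test approximation).

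**2. What each planned analysis covers.**

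| Analysis | All 178 women | Vaginal route | Time |
|---|---|---|---|
| Primary, time to delivery | yes | no | yes |
| Delivery within 12 and 24 h | yes | no | yes |
| Cesarean rate, indication | yes | yes | no |
| Time to active labor | incomplete if cesarean comes first | no | yes |
| Cesarean-excluded analysis | no | yes | yes |

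No row has all three. This and the order of events (randomisation, then labor, then a cesarean decision by unblinded providers) establish the structural point without any simulation.

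**3. Size, as an illustration.** These inputs are assumptions, not document figures:

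- latent time to vaginal delivery is lognormal, with mean 18 h (the protocol's mean) and SD 8.5 h;
- cesarean is 20% in the reference arm;
- the log-odds of cesarean rise by 1 or 2 per SD of log time.

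There were 4,000,000 women per arm. Entries are differences in mean hours, true → after exclusion.

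| Scenario | Slope 1 | Slope 2 |
|---|---|---|
| 6-h arm slower in proportion, its cesarean rising to 25% | 2.93 → 2.31 | 1.88 → 1.14 |
| Same, rising to 30% | 5.90 → 4.56 | 3.75 → 2.22 |
| 6-h arm slower by constant hours, rising to 25% | 2.90 → 2.78 | 2.07 → 1.76 |
| Same, rising to 30% | 5.69 → 5.47 | 3.90 → 3.31 |
| 6-h arm 4 h faster in proportion, cesarean falling to 13.2% / 10.4% | 4 → 3.30 | 4 → 2.73 |
| 6-h arm 4 h faster, 20% cesarean in both arms | 4 → 3.66 | 4 → 3.46 |
| No speed effect, 25% cesarean in 6-h arm | 0 → 0.32 favouring 6 h | 0 → 0.44 favouring 6 h |
| No speed effect, 30% cesarean in 6-h arm | 0 → 0.62 favouring 6 h | 0 → 0.85 favouring 6 h |

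Proportional slowing loses 21–41% of the difference (for example (3.75 − 2.22)/3.75 = 41%). Constant-hours slowing loses 4–15%. Under the trial's own hypothesis the loss is 0.70/4 = 17.5% to 1.27/4 = 32%.

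Putting the excess cesareans in the 12-h arm mirrors the last two rows (0.31–0.43 h and 0.63–0.85 h favouring 12 h). With no speed effect and equal rates, or with cesarean unrelated to labor speed and no speed effect, the difference is 0.0 h.

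A separate model (gamma times, correlation 0.3–0.7 between latent time and cesarean) gave 0.34–0.80 h for no speed effect at 30% against 20%, in line with the last row.

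**4. At the trial's size.** These are 4,000 simulated trials of 89 per arm, two-sided 0.05, Mann-Whitney test.

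- Proportional slowing to 30% cesarean: the excluded analysis favours 12 h in 51–91% of trials and 6 h in 0.0%, so it weakens the result without reversing it.
- No speed effect, 30% against 20%: it favours 6 h in 7–11%, where 2.5% would be nominal in that direction.
- 4 h faster with cesarean following: it favours 6 h in 84–88%, against 95% for the any-route test.

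**The case against.** The strongest reply is that the trial asks about time to delivery by any route and answers that question by intent to treat. The exclusion is openly called a sensitivity analysis. Cesarean rate and indication are pre-specified, so an imbalance will be visible. On this view, time to vaginal delivery in everyone is a reviewer's extra question, and only a labelling remark remains.

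Much of this stands. The primary is sound, and the weakness is confined to a supporting analysis. The sizes also need these qualifications:

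- **Scale.** With equal 20% cesarean, a 4 h benefit still shows as 3.66 or 3.46 h while the time ratio stays at 0.778, so part of the loss under the trial's hypothesis is a matter of scale. On the ratio scale the proportional-slowing loss is 12–27%, and the constant-hours loss is −3% to +4%.
- **Fewer women.** A random 71 per arm, with no selection, gives 89–91% power in the 4 h scenario. About half or more of the fall from 95% to 84–88% is therefore lost numbers. The 95% also depends on how cesarean times are generated; setting them equal to the latent vaginal time gives 95–96%.
- **Target.** The yardstick is a latent time as if cesarean did not occur. The protocol does not target it, and a cumulative incidence does not estimate it.
- **Inputs.** SD, distribution, dependence and arm-specific rates are all assumed.

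None of this restores randomisation to the excluded comparison. Nor is it a marginal analysis in the plan's own terms, because the sample was raised from 71 to 89 per arm for it. A separate cesarean rate shows that selection may differ between arms, but not what it did to the times.

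**Conclusion.** The concern holds on both counts: the cesarean-excluded analysis is not a randomised comparison, and no listed analysis combines vaginal route and time in all 178 women. Confidence in that is high, because it follows from the text.

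The size is conditional on the assumed inputs and modest against the 4 h target: roughly a fifth to two-fifths of a proportional difference hidden in mean hours, less on other scales, or an apparent difference of 0.3–0.9 h where there is no speed effect but cesarean rates differ. Direction cannot be fixed in advance, since the protocol gives a reason for longer labor in the 6-hour arm and also expects longer labor in the 12-hour arm. The primary conclusion is not threatened. This should be fixed, but it does not invalidate the trial.

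**What to change.** - Keep the any-route intent-to-treat primary, and state that cesarean counts as delivery in it. At the implied SD, all 89 per arm give it about 88% power.
- Add a supportive analysis of time to vaginal delivery in all 178 randomised women with cesarean as a competing event: cumulative incidence curves by arm, and differences in vaginal delivery by 12 and 24 hours with 95% confidence intervals.
- Keep the cesarean-excluded analysis if wanted, labelled descriptive, with the number excluded in each arm.
- Read these beside the planned cesarean rate, indication and time to active labor.

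**Cost.** Only analysis text changes. Time to delivery and cesarean are already planned outcomes, and the sample size stays.

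The added analysis mixes speed with cesarean frequency and is imprecise. The 95% interval for the difference in vaginal delivery by 24 hours is about ±12–14 points with 89 per arm. Under the same assumed model:

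- **No speed effect, 30% against 20% cesarean.** The 7-point fall in vaginal delivery by 24 hours reaches significance in only 16–17% of trials and Gray's test in 19–24%, less than the planned cesarean-rate comparison (32–34%).
- **4 h shortening, equal cesarean rates.** Gray's test has about 33–37% power, against about 95% or more for the any-route rank test.
- **4 h shortening, cesarean falling with it.** Gray's test has 72–86% power.

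It should be read from curves and intervals and must not replace the primary.

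### The serious-event review is worded toward a finding of unrelated, and early stopping is ruled out in advance, so no planned internal route leads from a related event to a change in conduct

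*Combined protocol and SAP*

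**What the plan says.** Monitoring and Quality Assurance sets four rules.

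- On interim looks and stopping: "We will not perform any interim analysis, as we feel there is minimal risk from the study protocol and would not stop the study early".
- On adverse events in general: when they "occur they will be reported to the Partners' IRB within 5 days with a detailed description of the event".
- On which events get a further review: "Serious adverse events (severe hemorrhage, maternal death, neonatal death, neonatal hypoxemic encephalopathy".
- On that review: these events "will be reviewed by the head of labor and delivery and the study staff to ensure the outcome is not related to the study protocol".

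The principal investigator also checks each participant's entries, but for completeness. No other safety review is described.

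Risks and Discomforts calls the added risk minimal and then names possible harms of the experimental arm: "Upon removal of the catheter at 6 hours the cervix may not be ripened and therefore increase the risk of prolonged induction and ultimately cesarean". If that arm takes longer to deliver, "it may also be associated with increased blood loss and risk of infection, which are known risks of prolonged induction". It offers a mitigation: "Our study, however, allows physicians to manage labor as deemed appropriate after foley removal".

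Biostatistical Analysis makes cesarean a secondary outcome ("Secondary maternal outcomes will be measured including cesarean delivery rate"). Subject Enrollment says that neither patients nor providers are blinded.

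**The concern.** A relatedness review should be able to return either answer. As written, its aim is to confirm that the event was unrelated. Study staff share the judgement, nothing in the protocol masks them to arm, and Risks and Discomforts records that the team expects the 6-hour arm to do better. The text does not say what happens if an event is judged related, and the no-stopping clause suggests that nothing would.

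Two things are at stake. First, randomisation would continue after a related serious event without any stated point at which someone in the trial must decide whether it should. Second, a later report that no serious event was related to the protocol would carry little weight, given who judged it and under what instruction.

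There is also a gap in coverage. Cesarean, the harm most directly foreseen, is not a reviewed event. Reviewing single cases could not show that a common event has become more frequent in one arm.

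**Working it through.** **1. The plan's own figure.** 71 / (1 − 0.20) = 88.75, rounded up to 89 per arm; 2 × 89 = 178. This agrees with Biostatistical Analysis. The base of 71 needs a standard deviation that is not stated (about 8.45 to 8.50 hours returns 71), but nothing below depends on it.

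**2. Foreseen harms against the review list.**

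| Harm named in Risks and Discomforts | Triggers review? | Where it is collected |
|---|---|---|
| Prolonged induction | No | Primary outcome, time to delivery |
| Cesarean | No | Secondary outcome |
| Blood loss | Only as severe hemorrhage | Maternal composite |
| Infection | No | Maternal composite (endometritis, wound infection) |

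One of the four is on the list, and only in its severe form.

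**3. Following one related event through the text.** The event occurs; it is reported to the IRB within 5 days; the head of labor and delivery and study staff review it. The text ends there. No grading of relatedness, no action and no decision-maker is given, and the no-stopping clause stands.

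**4. Following a rise in a common event.** At the plan's 20%, 0.20 × 89 = 17.8 cesareans are expected per arm in any case. Only a count by arm can show an excess over that, and none is planned before the end.

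**5. Scale, as illustration.** Inputs: 20% for the 12-hour arm (the plan gives 20% for all patients, so using it for one arm is an assumption); 30%, 35% or 40% for the 6-hour arm (assumptions); a look at 45 per arm, about half of 89. Excess over the whole trial = (p − 0.20) × 89; excess in the second half = (p − 0.20) × 44.5. The flag is z = (p̂₆ − p̂₁₂) / √(2p̄(1 − p̄)/45), with p̄ the mean of the two observed proportions. Its probability is the sum, over all pairs of binomial counts that exceed the threshold, of the product of their probabilities.

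| 6-hour rate | Excess, whole trial | Excess, second half | P(z > 1.96) | P(z > 1.645) |
|---|---|---|---|---|
| 20% | 0 | 0 | 0.027 | 0.053 |
| 30% | 8.9 | 4.45 | 0.201 | 0.303 |
| 35% | 13.35 | 6.7 | 0.369 | 0.494 |
| 40% | 17.8 | 8.9 | 0.563 | 0.679 |

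If enrolment ended at once whenever the flag fired, the expected number of cesareans avoided would be:

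- at 30%: 0.201 × 4.45 = 0.9 (z > 1.96) or 0.303 × 4.45 = 1.3 (z > 1.645);
- at 40%: 0.563 × 8.9 = 5.0 or 0.679 × 8.9 = 6.0.

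A single halfway look therefore does little unless the rise is large. These probabilities describe a test with a threshold; they do not carry over to a descriptive table without one.

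**The case against.** The strongest defence has four parts.

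- *The IRB is told.* Adverse events go to the IRB within 5 days, so an outside body could act. This stands, and it defeats the inference a reader might draw that a rise in harm could not change conduct before all 178 women are enrolled. It is a weak route for cesarean: reports are event by event, and the protocol does not say whether a cesarean is reportable, whether the IRB sees totals by arm, or what it would do.
- *Minimal risk is argued, not just asserted.* Risks and Discomforts sets physician discretion, other ripening agents and the expectation that the 12-hour arm will be slower against the harms it names. Blood loss and infection are raised only on condition that the 6-hour arm takes longer. So the two sections do not contradict each other. But discretion protects the individual woman; it does not detect a difference between arms, and it is no reason to rule out stopping.
- *The review wording may be loose drafting* for assessing whether an event is related. That is quite possible, and a reader should not infer a deliberately predetermined review. The text still needs correcting, because it is the instruction reviewers will follow.
- *No interim analysis is a reasoned choice* in a 178-woman trial of a routinely used device. This stands. The low flag probabilities support it, and the documents do not support reading its absence as a defect.

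**Conclusion.** The point holds in a limited form. The serious-event review is phrased to confirm unrelatedness, study staff share the judgement in an open-label trial, no consequence is attached to a related event, and early stopping is disclaimed in advance. IRB reporting is the only external check. No internal route is planned by which a related serious event, or a rise in cesarean in one arm, would change conduct.

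This is a weakness of safety governance. No figure in the plan is wrong, and the primary comparison is untouched. Its size cannot be derived from the documents. The illustration of about 9 to 18 excess cesareans over the full trial rests on assumed 6-hour rates of 30% to 40% against 20%. It shows what could accumulate unseen, not what is expected, and most of it would not be averted by one halfway look. The case for change therefore rests on the wording and not on those numbers.

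**What to change.** In Monitoring and Quality Assurance:

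1. Restate the purpose of the review as *to judge whether the event is related, possibly related or unrelated to the study protocol*. The head of labor and delivery makes the judgement; study staff supply the case facts only. The documents do not show that this person is blinded or independent of the study, so the change removes shared judgement but does not create an independent monitor.
2. Keep the statement that there is no interim analysis, specified as applying to the primary outcome. Delete the clause that disclaims early stopping, and state that enrolment may be paused and the matter referred to the IRB after a related or possibly related serious event.

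The cost is an amendment to two sentences and a small chance of an unnecessary pause. Time to delivery is not compared early, so the type I error of the primary test is unaffected.

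Optional: a descriptive count of cesarean by arm at about 89 deliveries, for harm only. Changes 1 and 2 do not by themselves address a rise in cesarean, since cesarean is not a listed serious event. A count would address it only if the protocol also said who acts on it and how. Its sensitivity would be limited: for scale, a z > 1.96 flag at 45 per arm fires with probability 0.20 for 20% v 30% and 0.56 for 20% v 40%. The morbidity composites should be left out of such a count, because outcomes run to 4 weeks after delivery and would be incomplete at that point.
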